Continuous variables will be displayed descriptively using the minimum and maximum values, mean values and standard deviation. Categorical variables will be presented descriptively using absolute and relative frequency as well as graphically using a pie chart.

Kolmogorov-Smirnov or Shapiro-Wilk test, depending on sample size, will be used to check the normality of data distribution, as well as graphical method of using histogram. If the data follow the normal distribution, parametric tests will be used for the statistical analysis of the data; otherwise the corresponding non-parametric tests will be used.

For the analysis of significant continuous variables over time, the Paired Samples t Test will be used if the data follow a normal distribution or the Wilcoxon test if the data do not follow the normal distribution. Significant results will be presented graphically using a bar chart or boxplot.

For the analysis of significant difference of continuous variables between the control and experimental groups, the Independent Samples t Test will be used if the data follow a normal distribution or the Mann-Whitney test if the data do not follow the normal distribution. Significant results will be presented graphically using a bar chart or boxplot.

For the analysis of the dependence between two continuous variables, the value of Pearson's or Spirman's correlation coefficient will be interpreted. In the case of strong correlations, the dependence will be shown both by the regression equation and graphically using the scatterplot.

For the analysis of the dependence between the two categorical variables, a Chi-squared test, that is, a Fisher's exact-dependency test will be used. The results will be presented graphically using a bar cluster graph.

The results will be considered statistically significant if the p value is less than 0.05.

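### A normality check on undefined data chooses between mean-based and rank tests, so the quantity compared between arms is not fixed before the outcomes are seen

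*Combined protocol and SAP*

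**What the plan says.** All the relevant text is in the section Statistical analysis plan of the combined protocol and SAP.

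- **The check:** "Kolmogorov-Smirnov or Shapiro-Wilk test, depending on sample size, will be used to check the normality of data distribution", and "as well as graphical method of using histogram".
- **The rule if the check passes:** "If the data follow the normal distribution, parametric tests will be used for the statistical analysis of the data".
- **The rule if the check fails:** "otherwise the corresponding non-parametric tests will be used".
- **Over time:** "the Paired Samples t Test will be used if the data follow a normal distribution or the Wilcoxon test".
- **Between groups:** "the Independent Samples t Test will be used if the data follow a normal distribution or the Mann-Whitney test".
- **Threshold:** "The results will be considered statistically significant if the p value is less than 0.05".
- **Description:** "Continuous variables will be displayed descriptively using the minimum and maximum values, mean values and standard deviation".

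No other section names a test for PANSS, the Heidelberg scale, MoCA, CRP, sedimentation or any cytokine.

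**The concern.** The t-test compares means. The Mann-Whitney test compares how often a value in one arm exceeds a value in the other. These are different questions, and under this rule the observed distribution decides which is asked.

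The rule also leaves several choices to the analyst:

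- which normality test applies at this sample size;
- what level makes the check fail;
- whether the test or the histogram prevails if they differ;
- whether the values checked are raw scores, changes, each arm or both arms pooled;
- what follows if one arm or visit passes and another fails.

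Two competent analysts could follow the plan and run different tests on the same data. This matters because the third working hypothesis (Objective and hypotheses) draws its scientific conclusion from whether the change in soft signs is significant. In addition, a variable sent to a rank test would still be summarised by mean and SD, so the p-value would stand beside means that it did not compare.

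**Working it through.** **Inputs.** The documents give 100 to 120 patients in total (Background), two parallel arms (Clinical Trial Design) and p < 0.05. They give no power calculation, SD or distribution, so there is no figure to reproduce. Assumed here: 1:1 allocation (50 to 60 per arm), two-sided tests, pretest level 0.05, and Kolmogorov-Smirnov (K-S) with the Lilliefors correction for estimated mean and SD. The shapes below are also assumed.

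**Simulation.** 4,000 trials per cell, with the same distribution in both arms. The rule was applied as: Mann-Whitney if Shapiro-Wilk fails in either arm, otherwise the equal-variance t-test. The Monte Carlo standard error near 5% is √(0.05 × 0.95 / 4000) = 0.3 points. Entries are percentages for 50 / 60 per arm.

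| Shape | Shapiro-Wilk and K-S disagree on one arm | One arm passes, the other fails (Shapiro-Wilk) | Pooled and per-arm checks choose different tests | Type I error of the rule | t and Mann-Whitney verdicts differ, no effect |
|---|---|---|---|---|---|
| Normal | 5.7 / 6.0 | 9.7 / 9.3 | 9.0 / 8.8 | 4.5 / 5.2 | 1.9 / 1.8 |
| Gamma, skewness 0.71 | 25.2 / 29.9 | 48.3 / 48.5 | 17.5 / 14.4 | 5.0 / 5.2 | 2.4 / 2.6 |
| Gamma, skewness 1.0 | 34.6 / 37.7 | 42.1 / 33.8 | 6.4 / 3.7 | 5.2 / 4.7 | 2.6 / 2.4 |
| t with 6 df | 18.8 / 21.1 | 40.4 / 44.5 | 14.7 / 14.0 | 4.7 / 5.0 | 2.8 / 2.9 |
| Log-normal, log-SD 0.5 | 21.4 / 22.0 | 14.0 / 6.9 | 0.5 / 0.1 | 5.0 / 4.9 | 3.2 / 3.4 |

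**Check of the third column.** If one arm fails with probability p, the arms split with probability 2p(1 − p). At skewness 1.0 and 50 per arm, at least one arm failed in 91.2% of trials. So p = 1 − √(1 − 0.912) = 0.703, and 2 × 0.703 × 0.297 = 0.418, against 0.421 simulated.

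**False switches.** For k independent, truly normal outcomes, the chance that at least one is sent to a rank test is 1 − 0.95^k with one check each. For k = 4 this is 1 − 0.95⁴ = 18.5%. With one check per arm it is 1 − 0.95⁸ = 33.7%.

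**Which values are checked.** A paired t-test relies on the differences. With a skewed trait and a normally distributed change, Shapiro-Wilk flagged the raw values in 74 to 79% of samples across separate runs, but the differences in only 4 to 5%. Checking raw values can therefore move a valid paired t-test to Wilcoxon.

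**Verdicts with a true effect.** For mildly skewed scores with a true shift of about half an SD, the t and Mann-Whitney verdicts differed in about 5 to 8% of trials.

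**Different spread, equal means.** With skewness 1.0 and an assumed 2:1 SD ratio, the rule rejected in 11.7% (50 per arm) and 13.7% (60 per arm) of trials. The t-test rejected in 4.5% and 5.5%. The excess arises because the rank branch tests a different quantity.

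**Power for a skewed marker.** For a log-normal marker (log-SD 1, ratio 1.75, 55 per arm), Shapiro-Wilk failed in every trial, so the rule always chose Mann-Whitney. Power was 80% under the rule against 82% for a log-scale t-test in one run, and 82% for both in another.

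**The case against.** Choosing a test by a normality check is familiar practice, and the case for tolerating it is substantial. Four stronger readings that a reader might infer are not supported.

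- **Inflated false positives.** With the same distribution in both arms, the rule's type I error was 4.5 to 5.2%. Even taking the smaller of the two p-values gave only 5.3 to 6.6%. The 12 to 14% rejection rate needs unequal spreads, and nothing in the documents establishes those.
- **Lost power.** A raw-scale t-test on the log-normal marker has only about 64% power, but the rule would almost never select it. Mann-Whitney is about as powerful as the log-scale test.
- **Two normality tests that give opposite answers.** At skewness 1.0, uncorrected K-S flags only 1 to 3% of samples, against about 70 to 78% for Shapiro-Wilk. The plan does not say which version of K-S it means. With the correction, the two tests often disagree but are not opposed.
- **Different tests in the two arms of the treatment comparison.** Each between-group comparison uses one test. Different tests by arm could arise only for the over-time analyses. That those are run within each arm is itself inferred from the working hypotheses, which speak of change in both groups. The split between arms in the table shows an ambiguous trigger for the switch, nothing more.

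The absence of an effect estimate is also not peculiar to the rank branch. The plan names no between-arm estimate or confidence interval on either branch, and a location shift can accompany a rank test.

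What stands is that the object of the check, its trigger and the resulting target quantity are all undefined, and that no analysis is named for any outcome.

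**Conclusion.** The point holds as one about an estimand that depends on the data and about analyst discretion. It is a cheap improvement, not a threat to the trial's validity. The text alone establishes that the choice is made from the outcome data and that the rule is incomplete. The sizes rest on assumed shapes, 1:1 allocation and a 5% pretest level: disagreement between the two normality tests in about 20 to 38% of moderately skewed samples, and different verdicts in about 5 to 8% of trials for mildly skewed scores with a true shift (2 to 3% with none). If the arms differ in spread, the rank branch can report a difference when the means are equal. How often that would matter here cannot be judged from the documents.

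**What to change.** Delete the normality switch, and name one between-arm analysis per outcome in the SAP before unblinding.

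- **PANSS, Heidelberg and MoCA:** the week-6 mean difference adjusted for the baseline value, with 95% CI. By the visit schedule in Clinical Trial Design, all three baselines are taken before randomisation.
- **CRP, sedimentation and cytokines:** the same model on log values, reported as ratios with 95% CI, with a stated rule for undetectable values.
- **Rank test:** a named sensitivity analysis only.
- **Reporting:** the between-arm estimate and CI for every outcome, whether significant or not.

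The cost is SAP wording, with no new patients, visits or measurements. The downside is a small efficiency loss for the mean-based test on skewed scores, about 1 to 6 power points in simulation; the rank sensitivity analysis would show whether the conclusion depends on it.

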Official Title: Aspirin as Adjuvant Therapy in Young Psychotic Patients NCT number: NCT02685748

Study Protocol and Statistical Analysis Plan

Effect of adjuvant aspirin therapy on neurological soft signs and PANSS in young psychotic patients

A randomized, interventional, double-blind, placebo-controlled clinical trial

Protocol name:	Aspirin2016.2
Date:	25 October 2016.
Donor:	Stanley Medical Research Institute, [name], [name] 20815, SAD
Sponsor:	Clinic for Mental Diseases "[name]", [name], Serbia
Principal Investigator, Grant Holder:	MD [name], psychiatrist
Co-investigators:	MD/PhD [name], neuropsychiatrist MD [name], psychiatrist MD [name], psychiatrist

Background:

The clinical trial team would conduct a randomized, interventional, double-blind, placebo-controlled study in two parallel groups of patients who were neuroleptically naive or previously minimally medicated (who did not take antipsychotics during the previous 6 months) with the illness duration of up to seven years. Patients of both sexes, ages 18 to 28, would participate in the trial, in accordance with the tenth revision of the International Classification of Diseases (ICD10), they would meet the diagnostic criteria for the illnesses ranging from F 20 to F 29. After meeting the inclusion and exclusion criteria and having signed an informed consent form, the patients would be randomized into two groups:

Experimental group - EG: antipsychotic + Aspirin

and

Control group – CG: antipsychotic + placebo.

The EG patients would be administered 1000 mg aspirin pro die with gastric protection pantoprazole 40 mg pro die, both medicines in two doses during 6 weeks of hospital treatment at Clinic form Mental Disorders "[name]". The trial would last for 18 months and would include the total of 100 to 120 patients.

Objective and hypotheses:

The objective of the trial would be to determine the effect of adjuvant aspirin therapy on neurological soft signs, positive and negative syndrome in schizophrenia, cognition, inflammatory factors and cytokine profile.

Working hypotheses:

- 1. Changes in PANSS and MoCA scores as well as inflammation factors in both patient groups, more in the experimental group.
- 2. Changes in the cytokine profile in both patient groups.

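### The SAP commits to no between-group difference with a confidence interval and graphs continuous comparisons only when significant, although hypothesis 3 draws a conclusion from non-significance

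*Combined protocol and SAP*

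**What the plan says.** The section Statistical analysis plan compares the arms on continuous outcomes by a test: "the Independent Samples t Test will be used if the data follow a normal distribution or the Mann-Whitney test". Its one stated criterion is "The results will be considered statistically significant if the p value is less than 0.05". It names no treatment difference, ratio or confidence interval for any outcome.

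The rule on graphs, "Significant results will be presented graphically using a bar chart or boxplot", appears twice, once for change over time and once for the comparison of the two groups. For correlations the rule is "In the case of strong correlations, the dependence will be shown both by the regression equation and graphically using the scatterplot"; what counts as strong is not defined.

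Other output carries no such condition. Continuous variables get minimum, maximum, mean and SD. Categorical variables get counts and percentages, and for the categorical analyses "The results will be presented graphically using a bar cluster graph". For correlations, "the value of Pearson's or Spirman's correlation coefficient will be interpreted", whatever its size. The SAP does not say that the descriptive statistics will be given by arm or by visit.

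Under Objective and hypotheses, the stated aim is to determine aspirin's effect on soft signs (SNS), PANSS, cognition, inflammation markers and cytokines. Working hypothesis 3 adds that if SNS show no significant change in the experimental group (EG), this will count in favour of SNS being a trait of schizophrenia.

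**The concern.** An objective to determine an effect calls for an estimate of that effect and its precision. The plan commits to a test result and leaves the estimate to be worked out from descriptive tables, if those turn out to be split by arm.

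The sharper problem is hypothesis 3. It converts a non-significant result into a scientific conclusion. A non-significant result can mean that any effect is too small to matter, or that the trial was too imprecise to tell. Only an interval separates the two, and the plan does not ask for one.

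The graph rule adds a second, smaller problem. A between-group figure appears only if the observed difference was large enough to be significant, so the figures are a selected set, and selection on significance pushes the differences shown upwards when the true effect is modest.

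**Working it through.** **Inputs.** From the Background section: the trial "would include the total of 100 to 120 patients", and "the patients would be randomized into two groups". From the SAP: significance at 0.05. The documents state no allocation ratio, sidedness of the test, dropout rate, effect size, SD or power. I assume 1:1 allocation (n = 50 to 60 per arm), a two-sided test and no dropout, and work in SD units. The sample size has no derivation, so there is no figure of the plan's own to reproduce.

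**Step 1: precision of an EG minus control (CG) difference.** The 95% half-width is t(0.975, 2n−2) × √(2/n).
- n = 50: 1.984 × 0.200 = 0.397 SD.
- n = 60: 1.980 × 0.183 = 0.362 SD.

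The same quantity is, to a close approximation, the smallest observed difference that can reach p < 0.05. An observed difference of 0.30 SD would therefore have an interval of −0.10 to 0.70 SD (N = 100) or −0.06 to 0.66 SD (N = 120). Under the present rule neither would be drawn.

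**Step 2: precision of a change within EG.** Hypothesis 3 can be read as referring to change within that arm alone. The half-width is then t(0.975, n−1) × √(1/n), in SDs of the change score.
- n = 50: 2.010 × 0.141 = 0.28.
- n = 60: 2.001 × 0.129 = 0.26.

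On either reading, a non-significant result leaves a range of non-zero effects open.

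**Step 3: difference detectable with 80% power.** (1.960 + 0.842) × √(2/n) gives 0.56 SD (n = 50) and 0.51 SD (n = 60). True effects below this will often be non-significant.

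**Step 4: what graphs limited to significant results would show.** I simulated 400,000 two-sample t tests per scenario. The observed difference was drawn from a normal distribution with mean d and standard error √(2/n), and the pooled variance from a scaled chi-squared distribution on 2n−2 degrees of freedom. I then averaged the absolute difference over the significant runs. The true effects d are assumptions.

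| True effect (SD) | Share significant, N = 100 / 120 | Mean significant difference (SD) | Ratio to truth |
|---|---|---|---|
| 0.2 | 17% / 19% | 0.50 / 0.46 | 2.5 / 2.3 |
| 0.3 | 32% / 37% | 0.52 / 0.48 | 1.7 / 1.6 |
| 0.5 | 70% / 78% | 0.60 / 0.57 | 1.2 / 1.1 |
| 0.8 | 98% / 99% | 0.81 / 0.80 | 1.01 / 1.01 |

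Hand check at d = 0.3, n = 50, treating the SD as known: (0.397 − 0.3)/0.2 = 0.485. The normal density there is 0.355 and the upper tail 0.314. The mean given significance is 0.3 + 0.2 × 0.355/0.314 = 0.53, in line with the simulated 0.52.

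**The case against.** The strongest reply is that the plan withholds less than it may seem to. Four stronger readings are tempting, and the documents do not support them.

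- *A reader might infer that the trial will be unable to state the size of aspirin's effect.* Means, SDs and correlation coefficients are planned without condition. If the means and SDs are given by arm, an unadjusted difference follows, with standard error √(s₁²/n₁ + s₂²/n₂), and SPSS prints the difference and its interval with the planned t tests. What remains is that the SAP does not commit to reporting these and does not say the descriptives are by arm or visit. The gap is wider for outcomes sent to Mann-Whitney, where mean and SD summarise poorly and no median or location shift is planned.
- *A reader might infer that non-significant results are suppressed.* The condition covers graphs of continuous comparisons, and for correlations the regression equation and scatterplot. Nothing removes non-significant outcomes from tables or text, and the categorical graphs, pie charts and histograms are unconditional.
- *A reader might infer that the graphs will exaggerate.* That depends on a true effect the documents do not give. At 0.8 SD the exaggeration is about 1%.
- *A reader might infer that an observed zero leaves a medium-sized effect open.* By the usual convention of 0.5 SD, it does not: half-widths of 0.36 to 0.40 SD around zero exclude it. They leave open effects up to about 0.4 SD in either direction.

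None of this answers hypothesis 3, where the inference rests on non-significance alone.

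**Conclusion.** The point holds in a limited form. The SAP commits to p-values and unconditional descriptives, not to a between-group difference with an interval for any outcome. It makes graphs of continuous comparisons depend on significance, and regression equations depend on an undefined strength of correlation. Combined with hypothesis 3, following the plan as written would allow a trait conclusion about SNS with no look at precision, which is more than a missing detail of presentation.

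The size is a half-width of about 0.40 SD (N = 100) to 0.36 SD (N = 120) for an EG minus CG difference. This rests on 1:1 allocation, a two-sided 0.05 test and no dropout; losses or unequal arms would widen it. The overstatement in graphs is a secondary matter, conditional on the true effect: considerable at 0.2 to 0.3 SD, slight at 0.5 SD and negligible at 0.8 SD. The plan should be changed, but the planned tests can still be run as they stand.

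**What to change.** Amend the Statistical analysis plan as follows.

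- For every outcome named in the objective, report the EG minus CG difference with its 95% confidence interval whatever the p-value. Where Mann-Whitney is used, report a location-shift estimate with its interval.
- Give descriptive statistics by arm and visit.
- Remove the significance condition on graphs, so that one rule applies to all continuous outcomes.
- Report every correlation coefficient analysed, with its interval, whether or not it is judged strong.
- Base any wording about no effect, or about SNS being a trait, on the interval and not on p ≥ 0.05. If hypothesis 3 keeps its reference to change within EG, give the interval for that change as well. State before unblinding what size of SNS difference would be too small to matter.

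Complete reporting in a table would be enough; a single figure of all outcomes is optional. The cost is SAP wording, output that SPSS already prints for the t tests, one extra step for the Mann-Whitney outcomes, and a short calculation for the correlation intervals. No new data or patients are needed.

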- 3. In case of significant change of SNS and cytokine profile in the experimental group the results would support the cytokine hypothesis. If there were no significant changes in the SNS in the experimental group, the results would support the SNS as a trait of schizophrenia.

Clinical Trial Design:

A randomized, interventional, double-blind, placebo-controlled clinical trial in two parallel groups of patients who were neuroleptically naive or previously minimally medicated (who did not take antipsychotics during the previous 6 months) with the illness duration of up to seven years. Patients of both sexes, ages 18 to 28, would participate in the trial, in accordance with the tenth revision of the International Classification of Diseases, would meet the diagnostic criteria for the illnesses ranging from F20 to F29. Upon fulfilment of inclusion and exclusion criteria and signed Informed consent form, they would be randomized in two groups: experimental (EG) and control group (CG). Patients belonging to the control group would be administered antipsychotic therapy and placebo, whereas patients in the experimental group would be administered regular antipsychotic therapy and aspirin. EG patients would be administered 1000 mg aspirin pro die with gastric protection- pantoprazole 40 mg pro die, both medicines in two doses in duration of 6 weeks.

A software application specialized in the randomization of subjects for clinical trials -*Sealed Envelope* - will be used for randomization. The obtained list will be in possession of one co-investigator and only he or she will know which group the patient belongs to. Only upon completion of the trial, after taking the serum samples from the last patient, and cytokine profile analysis (cytokine profile analysis would be performed at the end of the trial, after the serum sample from the last patient was taken at both test times) would the patient's belonging to the EG or CG group be revealed.

The co-investigator in charge of randomization would give out the medicine boxes and the medicines would all look identical - packed in the same capsules for overcapsulation by the company **Capsugel**. Placebo tablets would be manufactured by Galenika A.D. The patient would be administered Bayer's Aspirin tbl. á 500 mg and Nolpaza tbl. á 20 mg produced by Krka-Farma D.O.O.

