Three visits are planned. The first visit after admission to the Clinic. If the patient fulfils the inclusion criteria and none of the exclusion criteria (anamnestic data, somatic and psychiatric examination), and after the Informed consent form has been signed, PANSS scale test and blood sample would be taken for laboratory analysis. Laboratory analysis would be complete blood count (RBC, WBC, PTC, Hgb, Hct), sedimentation, C reactive protein, blood biochemical analysis (glycaemia, cholesterol, triglycerides, transaminases, CK, bilirubin, uric acid, creatinine, urea), and electrolytes (Na, K). Th1, Th2 and Th17 cytokines would be subject to the immunological assays. Each patient would be given an identification number (from one upwards) and the tubes with serum for the cytokine profile would be labelled with the same number, in terms of x/y, where x is the patient's identification number and y- may be "1" or "2" ("a" or "b"), where "1" or "a" would mean the first blood draw (at the beginning of the trial) and the number "2" or "b" - the second blood draw (at the very end of the trial).

After calming down of the acute signs of psychosis, between the third and fifth day of hospitalization, the second visit would be made when testing of the neurological soft signs would be performed according the Heidelberg Soft Neurological Signs Scale, the MoCA Cognitive Assessment Scale, and then the patient would be randomized to an experimental or control group if he/she meets the inclusion and no-exclusion criteria, if there are no somatic contraindications (with a stable ECG), and if he/she still wishes to participate in the trial.

The staff of the ward where the patient would be accommodated would be given two boxes of medicines labelled "Clinical Trial Medication 1" and "Clinical Trial Medication 2" that would be administered to patients – one medicine from each box, in the morning and in the evening.

After 6 weeks from the second visit (+/- 3 days), the third visit would be made when the patient would be examined, the PANSS, MoCA and Heidelberg scales testing repeated, and the blood sample taken again for laboratory analyses - inflammatory factors and cytokine profiles.

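### The between-arm comparison of continuous outcomes ignores baseline values already collected before randomisation; ANCOVA would usually be more precise at no extra data cost, and the analysed variable should be named.

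*Combined protocol and SAP*

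**What the plan says.** In the section Statistical analysis plan, the between-arm rule for continuous outcomes reads: "For the analysis of significant difference of continuous variables between the control and experimental groups, the Independent Samples t Test will be used" when data are normal, with Mann-Whitney otherwise. A general rule earlier in that section sends non-normal data away from parametric methods: "otherwise the corresponding non-parametric tests will be used". No covariate is named. The other methods listed do not fill the gap: the paired t and Wilcoxon tests look at change over time, and the regression equation serves only to describe strong correlations.

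The section does not say which variable is compared between arms. The working hypotheses help in part:

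- Hypothesis 1: "Changes in PANSS and MoCA scores as well as inflammation factors in both patient groups, more in the experimental group". This points to change.
- Hypothesis 2: "Changes in the cytokine profile in both patient groups". This makes no between-arm statement.
- Hypothesis 3: "In case of significant change of SNS and cytokine profile in the experimental group the results would support the cytokine hypothesis". This speaks of change within one arm.

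Under Clinical Trial Design, baselines come before allocation. At visit 1, "PANSS scale test and blood sample would be taken for laboratory analysis", and "Th1, Th2 and Th17 cytokines would be subject to the immunological assays". At visit 2 the Heidelberg scale is given, followed by "the MoCA Cognitive Assessment Scale, and then the patient would be randomized to an experimental or control group". All of these measures are repeated at visit 3, six weeks after visit 2.

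**The concern.** Every outcome in the objective has a pre-randomisation value, yet the between-arm test makes no model-based use of it. A comparison of visit-3 values discards the baseline. A comparison of changes gives the baseline a fixed weight of one, whatever its real correlation with the outcome. ANCOVA estimates that weight. With 100 to 120 patients, the precision given up could matter.

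The second issue is smaller. Visit-3 values and changes are different analyses, and which is more precise depends on a correlation that the documents do not give. The 5% error rate holds for either one alone, fixed in advance, but not for a choice made after seeing both.

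**Working it through.** **Inputs from the documents.** Total of 100 to 120 patients (Background); significance at p below 0.05 (Statistical analysis plan). The sample size comes without effect size, SD or power, so there is no planned power figure to reproduce.

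**Assumptions not in the documents.** 1:1 allocation, two-sided testing, no dropout, n = 50 per arm, true difference 0.5 week-6 SD, baseline to week-6 correlation r = 0.3/0.5/0.7, and s = baseline SD / week-6 SD = 1 unless stated.

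**Relative variance v of the arm difference.**

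- Week-6 value: v = 1
- Change: v = 1 + s² − 2rs, which is 2(1 − r) at s = 1
- ANCOVA: v = (1 − r²) × [1 + 1/(2n − 4)], where the last factor is the cost of estimating the covariate (1 + 1/96 = 1.0104 at n = 50)

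**Power** is from the noncentral t with noncentrality 0.5 / √(2v/n), on 2n − 2 degrees of freedom (2n − 3 for ANCOVA). Examples at n = 50: week-6, 0.5/√0.04 = 2.50; change at r = 0.3, v = 1.4, 0.5/√0.056 = 2.11; ANCOVA at r = 0.5, v = 0.75 × 1.0104 = 0.758, 0.5/√0.0303 = 2.87.

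| Analysis (50 per arm, s = 1) | r = 0.3 | r = 0.5 | r = 0.7 |
|---|---|---|---|
| Week-6 value | 70% | 70% | 70% |
| Change | 55% | 70% | 89% |
| ANCOVA | 73% | 81% | 93% |

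At 60 per arm the rows are 78%, 63/78/94% and 81/88/97%.

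**Variance saved by ANCOVA, after covariate cost, 50 per arm.**

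- Against week-6 values: 1 − (1 − r²) × 1.0104 = 8.1/24.2/48.5%.
- Against change, s = 1: 1 − (1 − r²) × 1.0104 / [2(1 − r)] = 34.3/24.2/14.1%.

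**Where the gain disappears.** Against week-6 values, break-even is r² = 1 − 1/1.0104, so r is about 0.10. Against change, when s = r the change variance is 1 + r² − 2r² = 1 − r², the same as ANCOVA before cost, so ANCOVA then loses about 1%.

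**Skewed laboratory values (simulation, 50 per arm).** Assumed log-normal, log SD 1 at both visits, arm difference 0.5 log-SD, none undetectable. Mann-Whitney on raw change depends on the direction of effect and on what controls do.

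| Analysis | r = 0.3 | r = 0.5 | r = 0.7 |
|---|---|---|---|
| Mann-Whitney, week-6 value | 67% | 67% | 67% |
| Mann-Whitney, raw change: aspirin raises the marker, controls static | 53% | 66% | 86% |
| Mann-Whitney, raw change: aspirin lowers it, controls static | 40% | 52% | 72% |
| Mann-Whitney, raw change: both fall (control 0.5, aspirin 1.0) | 28% | 35% | 46% |
| Mann-Whitney, log change | 53% | 67% | 88% |
| ANCOVA of logs | 73% | 81% | 93% |

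**Open variable.** If week-6 and change comparisons were both run and either counted as positive, the simulated false-positive rate at 50 per arm is 9.0/9.1/9.3% per outcome with t-tests and 9.1/9.1/9.4% with Mann-Whitney, instead of 5%.

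**The case against.** The strongest reply is that nothing here is wrong: an unadjusted test in a randomised trial is valid, and the benefit of ANCOVA rests on r, s and an effect size that the documents do not give. That stands. The benefit can be negligible: at r = 0.7 and s = 0.8, change has 93.0% power against 93.2% for ANCOVA. PANSS, named in the title, is the least favourable case, because its baseline is taken before the acute signs settle and may predict week 6 poorly. It is still a legitimate pre-randomisation covariate, and the worst outcome of using it is a variance cost of about 1%.

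A second reply is that the variable is not really unnamed, since protocol and analysis plan form one document and hypothesis 1 speaks of changes that are larger under aspirin. That is fair for PANSS, MoCA and inflammation factors, although the analysis section does not repeat it. It does not cover soft signs or cytokines, whose hypotheses make no between-arm statement.

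A reader might infer that the investigators mean to try both comparisons and report the better one, and so that the error rate is inflated to 9%. The documents do not support this. They describe no such choice; they only fail to exclude it.

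**Conclusion.** The point holds as a free improvement in precision, with a secondary gap in specification. Under the stated assumptions ANCOVA lifts power at 50 per arm from 70% (week-6 values) or 55/70/89% (change) to 73/81/93%. Apart from about 1% for estimating the covariate, its variance exceeds neither alternative. For skewed markers the advantage over Mann-Whitney on raw change may be much larger, especially if both arms fall; undetectable values would reduce it.

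Two stronger readings should be resisted. A reader might infer that the planned test is biased or invalid; once its variable is fixed it is neither. A reader might also take the power figures to show that the trial is too small; they cannot, because no target difference or SD is stated and 0.5 SD is only an illustration.

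The change should be made, but the trial's validity does not depend on it.

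**What to change.** In the section Statistical analysis plan:

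1. State that the between-arm analysis of PANSS, Heidelberg soft signs, MoCA, inflammatory factors and each cytokine is an ANCOVA of the visit-3 value on arm and the pre-randomisation value of the same variable, reporting the adjusted difference with its 95% confidence interval. This also settles the analysed variable.
2. Log-transform all cytokines and C-reactive protein at both visits. List them in advance, so that the choice does not depend on skewness seen in the data. Fix one rule for undetectable values before unblinding, for example half the detection limit.
3. State that the general normality rule does not override this ANCOVA; as written, it would divert non-normal outcomes to an unadjusted test.
4. Name as the sensitivity analysis a Mann-Whitney test on change from baseline, using log change for the logged variables. Raw change would be a weak check for skewed markers.

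The cost is a few sentences in that section and slightly more analysis. No extra data, visits or patients are needed.
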